### 4.3. Rescreening Criteria

Subjects may be required to be rescreened as part of this study. Subject who are screen failures, due to transient exclusion criteria (ie, blood donations, consumption of products within last 28 days, etc), may be rescreened at the discretion of the Investigator, in consultation with the Sponsor.

A subject within the original screening window must meet all eligibility criteria with the following conditions:

- All Day -2 and/or Day -1 procedures (Table 6-1) must be repeated, if already done
- The subject will retain his/her original subject identification number

A subject outside of the original screening window must repeat all screening procedures, meet all eligibility criteria, and have a new subject identification number issued.

### 4.4. Withdrawal Criteria

### 4.4.1. Before First Treatment Administration

Before the first treatment administration, inclusion/exclusion criteria will govern the subjects to be dosed. If either the urine drug (except for THC) and alcohol screen or the naloxone challenge is positive, the subject will be excluded from the study. Subjects withdrawn before first treatment administration will not be followed up and will not undergo End-of-Study/Early Termination assessments. Other safety assessments may be performed if required.

Subjects are free to withdraw their consent to participate in the study at any time, without prejudice. The reason for their withdrawal or for deciding to end their participation will be documented.

#### 4.4.2. After First Treatment Administration

Subjects may, at any time, voluntarily withdraw from the study or be removed from the study at the discretion of an Investigator or Sponsor. An Investigator may withdraw a subject at any time for any (but not limited to) of the following reasons: if it is determined that continuing the study would result in a significant safety risk to the subject or if their behavior is deleterious to the study environment. If such withdrawal occurs, or if the subject fails to return for visits, an Investigator should determine the primary reason for a subject's premature withdrawal from the study and record the reason in the subject's study documents.

In the case of a clinically significant illness detected during the trial (including COVID-19 diagnosis), the Principal Investigator (or delegate) will, in consultation with the Medical Monitor and Sponsor Physician, determine the most appropriate course of action on an individual basis. Evaluations will include but are not limited to:

- The safety of the subject and other study participants
- The possible effect the illness would have on the results gathered during the trial, and their ability to be appropriately analyzed or interpreted
- The possibility of suspending participation then re-initiating it after recovery
- The implication of any inclusion or exclusion criteria that would contradict possible actions
- The implication of any adherence to regulatory guidelines that may be affected by actions decided; for example group effect analysis
- The sample size calculation, current number of subjects, and possibility of replacement subjects

Evaluations and decision-making for subject removal will be documented in the study file, reported to the Sponsor, and discussed where appropriate in the Clinical Study Report.

Attempts should be made to have such subjects complete the End of Study/Early Termination assessments. End-of-Study/ET assessments should be performed as soon as possible after the last study treatment administration.

For subjects lost to follow-up (ie, those subjects whose status is unclear because they fail to appear for study visits without stating an intention to withdraw), an Investigator should show "due diligence" by documenting in the source documents steps taken to contact the subject, eg, dates of telephone calls (at least 3), registered letters (at least 1), etc.

## 4.4.2.1. Stopping Rules

#### 4.4.2.1.1. Individual Subject Stopping Rules

Participation in the clinical study may be discontinued by an Investigator (or delegate) in charge of the study or by the Sponsor for any of the following reasons, but not limited to:

- AEs (including if a subject develops any significant illness or needs to undergo any major surgery during course of the study)
- Subject non-compliance (including any violation of protocol requirements which may affect the study outcome)

Subjects will be discontinued from the clinical study for any of the following reasons, but not limited to:

- Total serum bilirubin > 2x upper limit of normal (ULN)
- Aspartate aminotransferase (AST) > 3x ULN
- Alanine aminotransferase (ALT) > 3x ULN
- Creatinine > 1.5x ULN

## 4.4.2.1.2. Trial Stopping Rules

Clinical trial stopping rules:

- If 2 AZD4041-related (based on Investigator or Sponsor assessment) SAEs occur (Grade 3, 4, or 5)
- Occurrence of 1 death attributable to the study treatment
- At least 2 subjects who received AZD4041 have QTc prolongation defined as QTcF > 500 ms, or a prolongation from baseline of > 60 ms, confirmed (persistent for at least 5 minutes) and determined postdose either on 12-lead digital ECG (dECG) obtained during continuous 12-lead ECG monitoring or on a repeat 12-lead safety ECG
- At least 2 subjects who received AZD4041 have tachycardia defined as resting supine HR > 125 beats per minute persisting for at least 10 minutes
- At least 2 subjects who received AZD4041 have symptomatic bradycardia defined as resting supine HR < 40 beats per minute or asymptomatic bradycardia defined as resting supine HR < 30 beats per minute while awake persisting for at least 10 minutes
- At least 2 subjects who received AZD4041 develop hypertension defined as an increase in resting supine systolic BP > 40 mmHg and above 180 mmHg and persisting for at least 10 minutes
- At least 2 subjects who received AZD4041 develop hypotension defined as an asymptomatic fall in systolic BP > 20 mmHg and below 70 mmHg persisting for at least 10 minutes, or a symptomatic fall in resting supine systolic BP > 20 mmHg (excluding vasovagal reaction or where the Investigator considers this to be most likely related to morphine administration)

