Additional safety measures implemented at predose and specified timepoints postdose will include the collection and documentation of AEs and vital signs (ie, systolic and diastolic BP, HR, and oral temperature), respiratory rate, and SpO2. Cardiovascular risk mitigations include appropriate eligibility criteria, individual and study-level stopping criteria; and a sufficiently stringent level of cardiac monitoring will be retained for the current clinical study protocol, similar to MAD study protocol; 12-lead safety ECGs, alongside extended periods of ECG telemetry and Holter monitoring have been implemented to monitor for any arrhythmias. Subjects will be determined as eligible for inclusion into the study based on measures of clinical laboratory testing, vital signs, medical history, Columbia-Suicide Severity Rating Scale (C-SSRS), physical examination, and ECG.

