### 1.3.3. Risk/Benefit Conclusion

The hepatic and thyroid effects observed in the preclinical studies were considered minimal and adaptive; and thymic atrophy was noted to have fully recovered at the end of the recovery period. On the basis of data observed in the safety pharmacology study, the effects of AZD4041 co-administered with single doses of morphine, on respiratory drive will be evaluated and monitored in the clinical study by measuring EtCO2, O2 saturation, and respiratory rate.

Cardiac arrhythmia remains a *potential* risk during the ongoing exploratory clinical development of AZD4041 and appropriate risk mitigation measures have been implemented into the protocol.

Women of non-childbearing potential may be enrolled into the study. Inclusion of fertile (non-vasectomised) males in the study is justified on the basis that the 3-month dog GLP study provides the most robust and comprehensive evaluation of AZD4041 on the male reproductive tract in this species. A NOAEL has been identified in the dog study with respect to toxicologic effects seen in the prostate, testes and epididymides. Human exposures to AZD4041 at steady-state for the planned dose level (COV), once daily for 14 days) are not expected to exceed 1/10th of the NOAEL in the 3-month dog study. These exposures are also significantly lower than those identified at the NOAEL in the rat 1-month study. No reproductive effects have been seen in the rat 1-month GLP study. In addition, the planned dose of AZD4041 has been evaluated previously in a 14-day MAD clinical study; the dosing regimen was generally well tolerated and no significant medical or safety concerns were raised by the dose escalation committee.

Based on the considerations regarding the potential risks of AZD4041, exposure of healthy volunteer subjects with a history of recreational opioid use to repeat doses of AZD4041 is considered justifiable in relation to the significant unmet need to develop improved efficacious

treatments for opioid-use disorder. It is expected that the safety, tolerability and PK data acquired in the current study in healthy volunteer who are opioid users, will provide a scientific basis and rationale for the subsequent evaluation of AZD4041 in patients with OUD.

More detailed information about the known and expected benefits and risks and reasonably expected AEs of AZD4041 may be found in the Investigator's Brochure (AZD4041 Investigator's Brochure).

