## 6.1.15. Medical Interventions for Signs of Respiratory Depression

In the event that subjects show signs and symptoms of respiratory depression, the Investigator or study staff will begin intervention procedures that may escalate in the degree of intervention as follows:

- Verbal stimuli: Call the subject's name loudly. If no response and/or no improvement in respiratory depression, proceed to physical stimuli.
- Physical stimuli: Apply sternal rub to subject and/or apply nail bed pressure. If subject is unable to be aroused and/or there is no improvement in signs of respiratory depression, proceed to O2 administration and prepare for possible naloxone administration (if there is no improvement with verbal or physical stimuli, there is a high likelihood of requiring naloxone administration).
- O2 administration: Administer oxygen with a target SpO2 of 95-100%. Prepare naloxone for administration if no improvement in respiratory depression clinical parameters or as per Investigator discretion.
- Naloxone administration: Administer naloxone (eg, 4 mg/spray IN every 2-3 minutes; 0.4 mg IV every 2-3 minutes to a maximum of 10 mg) and titrate until adequate oxygenation/ventilation is achieved.

The Investigator or designee will choose the appropriate level of intervention as deemed medically necessary. Subjects who receive intervention will be evaluated to determine if further intervention (eg, hospitalization) is warranted. Subjects who show significant signs of respiratory depression that requires naloxone administration or poses significant safety concerns may be withdrawn from the study at the discretion of the Investigator or designee.

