#### 7. ADVERSE EVENTS DOCUMENTATION

#### 7.1. Definitions

An AE is defined as any untoward medical occurrence in a subject administered an IP and which does not necessarily have a causal relationship with the treatment. An AE can therefore be any unfavorable and unintended sign (including a clinically significant abnormal clinical laboratory finding, for example), symptom, or disease temporally associated with the use of an IP, whether or not related to the IP.

A suspected adverse reaction (SAR) is any AE for which there is a reasonable possibility the drug caused the AE. 'Reasonable possibility' means there is evidence to suggest a causal relationship between the drug and the AE. A suspected adverse reaction implies a lesser degree of certainty about causality than adverse reaction, which means any AE caused by a drug.

An AE may be:

- A new illness,
- Worsening of a concomitant illness,
- An effect of the study drug including comparator; it could be an abnormal clinical laboratory value as well as a significant shift from baseline within normal range which an Investigator considers to be clinically important.

Surgical procedures themselves are not AEs. They are therapeutic measures for conditions that required surgery. The condition for which the surgery is required is an AE, if it occurs or is detected during the study period. Planned surgical measures permitted by the clinical study protocol and the conditions(s) leading to these measures are not AEs, if the condition(s) was (were) known before the start of study treatment. In the latter case, the condition should be reported as medical history.

A SAE or reaction is any untoward medical occurrence that at any dose:

- Results in death,
- Is life-threatening,
- Requires inpatient hospitalization or prolongation of existing hospitalization,
- Results in persistent or significant disability or incapacity (defined as a substantial disruption of a person's ability to conduct normal life functions),
- Is a congenital anomaly or birth defect,
- Is an important medical event (including development of drug dependence or drug abuse) that may jeopardize the subject or may require intervention to prevent one of the other outcomes listed above (according to medical judgment of an Investigator)

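### No trial stopping rule names a respiratory event, so non-fatal respiratory depression as such counts towards a mandatory stop only when rated a Grade 3-4, AZD4041-related SAE and joined by a second related SAE

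*Protocol*

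**What the plan says.** Protocol 4.4.2.1.2 sets seven trial-level rules. Two are not tied to an organ system: "If 2 AZD4041-related (based on Investigator or Sponsor assessment) SAEs occur (Grade 3, 4, or 5", and "Occurrence of 1 death attributable to the study treatment". The other five concern QTc, tachycardia, bradycardia, hypertension and hypotension. Each fires when two AZD4041 subjects cross a limit, serious or not; for example, "At least 2 subjects who received AZD4041 have tachycardia defined as resting supine HR" above 125 beats per minute for at least 10 minutes. Four of these five have no cause condition. The hypotension rule has an exclusion for vasovagal reactions and for falls that the Investigator puts down to morphine.

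Respiratory limits appear elsewhere. Protocol 6.1.14 makes them capnography alarms, assessed and reported as AEs where applicable. Protocol 6.1.15 gives a ladder of interventions ending in naloxone. Of the treated subject it says "Subjects who receive intervention will be evaluated to determine if further intervention (eg, hospitalization) is warranted", and subjects with "respiratory depression that requires naloxone administration or poses significant safety concerns may be withdrawn from the study at the discretion of the Investigator".

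The risk section (1.3.2) states that "Cardiovascular risk mitigations include appropriate eligibility criteria, individual and study-level stopping criteria". For respiration, 1.3.3 says that effects "on respiratory drive will be evaluated and monitored in the clinical study by measuring" EtCO2, oxygen saturation and respiratory rate. The SAP adds no stopping rule. Its section 11 allows an optional blinded review near the end of the study.

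**The concern.** Protocol 1.3.2 reports that rats given morphine after AZD4041 had more respiratory depression. Section 2 makes respiratory drive the primary objective, and 1.3.2.1 chooses a supratherapeutic morphine dose to make respiratory effects easier to see. The hazard that the study exists to test therefore has no rule of the kind given to cardiovascular effects.

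Subgroups of at most 8 start at least 2 days apart (3.1), so Day 15 doses are staggered too. That spacing can protect later subjects if AZD4041 worsens morphine's effect, but no respiratory rule makes use of it.

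**Working it through.** **1. Rule by rule.**

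| Trial rule (4.4.2.1.2) | Can non-fatal respiratory depression as such meet it? |
|---|---|
| 2 AZD4041-related SAEs, Grade 3-5 | Yes, if serious, Grade 3-4 and rated related |
| 1 attributable death | No (fatal only) |
| QTc, tachycardia, bradycardia, hypertension, hypotension | No (only through a secondary ECG, heart-rate or blood-pressure change) |

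Seven rules, none respiratory, and one open to a non-fatal respiratory event. The second SAE may be of any kind, and relatedness may be judged by the Investigator or the Sponsor.

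**2. Is a naloxone rescue an SAE?** If it is not life-threatening and leads to no hospitalization, the relevant limb of the definition in 7.1 is an important medical event that "may jeopardize the subject or may require intervention to prevent one of the other outcomes listed above (according to medical judgment of an Investigator". A rescue could well be rated serious on that wording, but the rating is a judgment. A case in which no rule fires: two Sequence 1 subjects need naloxone on Day 15, neither did on Day 1, both recover in the unit, and both events are rated non-serious.

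**3. How much the rating matters.** The documents give no event rate, and no formal sample size calculation was done, so there is no stated figure to reproduce. Let p be the assumed share of the 28 AZD4041 subjects with such an event and s the assumed share of events rated serious, Grade 3-4 and AZD4041-related. The chance that the SAE rule fires through respiratory events alone is P(X ≥ 2), X ~ Bin(28, p·s).

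| p | s = 50% | s = 25% | s = 10% | Direct 2-subject rule (s = 100%) |
|---|---|---|---|---|
| 10% | 0.412 | 0.154 | 0.032 | 0.785 |
| 20% | 0.785 | 0.412 | 0.107 | 0.985 |

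A related SAE of another kind would raise the first three columns.

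**4. What a direct rule could save.** SAP 3.4 puts 4 × 1/2 = 2, then 8 × 5/8 = 5 (four blocks), then 8 × 3/4 = 6 Sequence 1 subjects in Blocks 1-6. Cumulative: 2, 7, 12, 17, 22, 28. Still without the combination: 26, 21, 16, 11, 6, 0. Assume that dosing subgroups follow the blocks. Let r be the assumed share needing naloxone on Day 15 but not on Day 1. With n the cumulative count, the rule has fired by the end of a block with probability P(X ≥ 2), X ~ Bin(n, r). Expected number spared = sum over blocks of P(first fires at that block) × number remaining.

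| r | Fired by Block 3 (n = 12) | Mean spared of 28 |
|---|---|---|
| 2% | 0.02 | 0.8 |
| 5% | 0.12 | 3.7 |
| 10% | 0.341 | 9.1 |
| 20% | 0.725 | 16.1 |
| 30% | 0.915 | 19.3 |

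These means are upper limits: they assume that the combination is never restarted.

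**5. False pauses from morphine alone.** If naloxone need is independent between days at rate p per dose, the chance of need on Day 15 only is p(1 − p): 0.0099, 0.0196 and 0.0475 for p = 1%, 2% and 5%. With X ~ Bin(28, p(1 − p)), P(X ≥ 2) = 0.031, 0.104 and 0.387; P(X ≥ 3) = 0.003, 0.017 and 0.146. If the same subjects are sensitive on both days, these chances fall, because the Day 1 condition removes such subjects.

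**The case against.** The strongest reply is that the SAE rule already covers the case. Naloxone is the last step of the ladder in 6.1.15, and rescue from opioid respiratory depression plausibly fits the important-medical-event wording. An Investigator who blames morphine does not close the rule, because the Sponsor's assessment of relatedness also counts. This stands in part. A reader might infer that the present rules would never fire on naloxone rescues, or that both SAEs must be respiratory. The documents support neither. The first is true only if every rescue is assumed non-serious, and the rule accepts any second related SAE.

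A reader might also infer that later subjects have no protection beyond someone's choice to stop. That is too strong. Protocol 4.4.2 requires the Principal Investigator to consult the Medical Monitor and Sponsor Physician about a clinically significant illness and to weigh the safety of other participants. Alarms, rescue and on-site cover (6.1.14 to 6.1.16) protect the subject being dosed, and 12.6 lets the Sponsor terminate at any time. But the consultation decides the course for an individual, and termination is discretionary. None of these requires a trial-level pause.

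The omission may be deliberate, since morphine is expected to depress respiration. That is a good reason not to use the primary-endpoint limits as triggers. It does not rule out a trigger based on new need for naloxone, with each subject's Day 1 as the reference.

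Finally, a general dosing pause would do harm. At the minimum 2-day stagger, when Block 1 reaches Day 15, Blocks 2-6 are on Days 13, 11, 9, 7 and 5. Stopping their oral doses could lose steady state, given the effective half-life of 18.6 to 21.3 hours (1.3.2). This stands, and it narrows the fix.

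**Conclusion.** The gap is real but limited. No trial stopping rule names a respiratory event, and non-fatal respiratory depression as such reaches a mandatory stop only through a rating as a Grade 3-4, AZD4041-related SAE plus a second related Grade 3-5 SAE. Followed as written, the plan can give later subgroups the combination after repeated new naloxone rescues. It does not follow that it would: the rescues may be rated serious, and the Sponsor may stop by choice.

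The gap itself rests on the text of 4.4.2.1.2 and needs no assumed rate. Its size does. The mean number spared runs from about 1 to 19 of 28 as new naloxone need goes from 2% to 30%, on the assumptions that subgroups follow the SAP blocks and the combination is not restarted. At low rates the gain is small. The change is still worth making, because the trigger uses data already recorded and leads to a review, not to the end of the trial.

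**What to change.** Add to 4.4.2.1.2: *Further Day 15 morphine co-administration is paused for safety review if at least 2 subjects who received AZD4041 need naloxone for respiratory depression on Day 15 and did not need it on Day 1; daily oral dosing of subgroups already started continues during the review unless the review decides otherwise.*

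Amend 5.2.4, which now allows the code to be broken only for emergency treatment or an SAE report, so that the existing designated holder of the randomization information may confirm allocation for the stopping rules. The AZD4041-specific rules already in the list need this too. No additional reviewer is needed.

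Costs: no new data, since interventions and rescue medication are already documented (6.1.14, 6.1.16). Day 15 may be delayed for later subgroups. A subject whose Day 15 is deferred while oral dosing continues would take more than the 14 planned doses, so the review should be short. The false-pause chance is about 3%, 10% or 39% at an assumed 1%, 2% or 5% naloxone need per dose. If that is thought too high, a 3-subject trigger lowers it to 0.3%, 1.7% or 15%, at the price of acting later.

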#### 4.5. Lifestyle and/or Dietary Requirements

- Subjects will be prohibited from consuming food or beverages containing grapefruit and/or pomelo for 7 days prior to the first dosing and during the study.
- Subjects will be prohibited from consuming alcohol for 48 hours prior the first dosing and during the study. They will also be prohibited from recreational drug use from screening until the follow-up visit. In case of any doubt, a test for alcohol and/or a drug screen may be performed if requested by an Investigator. If a subject presents with a positive alcohol test or drug screen at any time after the screening visit, the subject may be rescheduled at the discretion of an Investigator. If THC is positive at check-in, a cannabis intoxication evaluation will be done by an Investigator, and inclusion will be at his or her discretion.
- Subjects will be prohibited from consuming food or beverages containing xanthines (ie, tea, coffee, cola drinks, energy drinks or chocolate) for 48 hours prior to the first dosing and during the study.
- Subjects will eat only the food provided by the study site during confinement at the CRU.
- During the study, subjects who are smokers should not smoke more than 20 cigarettes per day. Subjects will abstain from smoking for 1 hour prior and until 6 hours after each drug administration.

• Subjects will be asked to refrain from driving, operating machinery, or engaging in hazardous activities until they and an investigator are convinced the study drug is not impairing their judgment and/or ability to perform skilled tasks.

